**Table 7 Objectives and endpoints**

Objectives	Endpoints
Primary: Investigator reported (eCRF)	
To determine the efficacy of prophylactic octreotide in reducing the proportion of subjects experiencing diarrhoea with a severity of NCI CTCAE Grade 2 and above.	Proportion of subjects experiencing diarrhoea with a severity of Grade 2 and above, as defined by the NCI CTCAE, version 4.03, recorded as AEs in the eCRF.
Secondary: Investigator reported (eCRF)	
To determine the efficacy of prophylactic octreotide in reducing the proportion of subjects experiencing diarrhoea with a severity of NCI CTCAE Grade 3 and above.	Proportion of subjects experiencing diarrhoea with a severity of Grade 3 and above, as defined by the NCI CTCAE, version 4.03, recorded as AEs in the eCRF.
To determine the efficacy of prophylactic octreotide in reducing the proportion of subjects experiencing diarrhoea of any grade of severity.	Proportion of subjects experiencing diarrhoea of any grade of severity as defined by the NCI CTCAE, version 4.03, recorded as AEs in the eCRF.
To determine the efficacy of prophylactic octreotide in reducing the duration of diarrhoea of any grade of severity.	Duration of diarrhoea of any grade of severity, recorded as AEs in the eCRF.
To determine the efficacy of prophylactic octreotide in increasing the time to onset of the first episode of diarrhoea of any grade of severity.	Time to onset of the first episode of diarrhoea of any grade of severity, recorded as an AE in the eCRF.
To determine the efficacy of prophylactic octreotide in reducing the proportion of subjects taking anti-diarrhoeal medication.	Proportion of subjects taking anti-diarrhoeal medication, recorded in the eCRF.
To determine the efficacy of prophylactic octreotide in reducing the proportion of subjects making unscheduled visits to healthcare professionals as a result of diarrhoea.	Proportion of subjects making diarrhoea-related unscheduled visits to healthcare professionals, recorded in the eCRF.
To determine the efficacy of prophylactic octreotide in reducing the proportion of subjects requiring changes in cancer therapy (dose delays, dose reductions and treatment withdrawal) as a result of diarrhoea.	Proportion of subjects requiring diarrhoea-related lapatinib and capecitabine dose reduction, dose delay and treatment withdrawal, recorded in the eCRF.

Objectives	Endpoints
Secondary: Investigator reported (eCRF)	

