To determine the efficacy of prophylactic octreotide in reducing the proportion of subjects requiring treatment with intravenous fluids resulting from diarrhoea.	Proportion of subjects requiring use of diarrhoea-related intravenous fluids for rehydration, recorded in the eCRF.
To determine the effect of prophylactic octreotide on compliance with lapatinib and capecitabine treatment.	Number of lapatinib and capecitabine tablets dispensed and returned, recorded in the eCRF.
To determine the effect of prophylactic octreotide on the efficacy of treatment with lapatinib and capecitabine.	Overall response rate and clinical benefit response measured in accordance with the Response Evaluation Criteria In Solid Tumours (RECIST) version 1.1.
To determine the effect of prophylactic octreotide on the safety and tolerability of cancer treatment.	Proportion of subjects with AEs and SAEs, recorded in the eCRF.

Objectives	Endpoints
Secondary: Patient reported (DMD)	

To determine the effect of prophylactic octreotide on patient-reported diarrhoea.
 
To determine the effect of prophylactic octreotide in delaying patient reported diarrhoea.
 
To determine the effect of prophylactic octreotide in reducing the proportion of patients taking anti-diarrhoeal medication.
 
To determine the effect of prophylactic octreotide in reducing the proportion of patients making dietary changes to control diarrhoea.
 
To determine the effect of prophylactic octreotide on the proportion of patients contacting other non-hospital healthcare professionals to discuss diarrhoea.
 
To determine the effect of prophylactic octreotide in reducing the proportion of patients reporting non-adherence due to diarrhoea.
	
Proportion of patients reporting changes in bowel movements from baseline (frequency and/or consistency), recorded in the DMD.
 
Time to the first patient reported change in frequency and/or consistency of bowel movements from baseline, recorded in the DMD.
 
Proportion of patients taking anti-diarrhoeal medication, recorded in the DMD.
 
Proportion of patients making dietary changes due to diarrhoea, recorded in the DMD.
 
Proportion of patients contacting other non-hospital healthcare professionals to discuss diarrhoea, recorded in the DMD.
 
Proportion of patients reporting stopping completely or missing doses of anti-cancer tablets due to diarrhoea, recorded in the DMD.

Quality of Life (FACIT-D)	

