#### **9.3.3.2. Other comparisons of interest**

This is an exploratory study, and the sample size may be insufficient to demonstrate statistical significance for the primary objective. The diarrhoea-related secondary objectives of the study will provide additional perspective to support the primary objective.

Assessment of disease progression in accordance with RECIST version 1.1 is required only at the end of study visit. Disease assessments during the course of treatment with lapatinib and capecitabine may be conducted in accordance with local practice, and there

will be some inconsistency between the data provided by different sites at these visits. The assessment of disease progression in LAP117314 will be limited by the sample size and by the variability in response assessments prior to the end of study visit, and may not be comparable with that reported in other studies.

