**Unscheduled visits to/contact with healthcare professionals**

The proportion of subjects requiring an unscheduled visit to or contact with a healthcare professional at least once as a result of diarrhoea will be summarised and analysed using the same method as described in Section 9.3.5.1.1 for the primary endpoint.

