**Subjects should be instructed to first notify their physician/healthcare provider at onset of diarrhoea of any severity.**

An assessment of frequency, consistency and duration as well as knowledge of other symptoms such as fever, cramping, pain, nausea, vomiting, dizziness and thirst should be taken at baseline. Consequently subjects at high risk of diarrhoea can be identified. Subjects should be educated on signs and symptoms of diarrhoea with instructions to report any changes in bowel patterns to the physician.

It is recommended that subjects keep a diary and record the number of diarrhoea episodes and its characteristics. They should also include information on any dietary changes or other observations that may be useful in the evaluation of their diarrhoea history.

If subjects present with diarrhoea of any grade, check they are taking lapatinib correctly, i.e. single daily dose, rather than splitting it through the day. . Obtain information on food (solid and liquid) and over the counter (OTC) medication, including herbal supplements, taken during the lapatinib treatment period.

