- Cycle 2 to be started 21 days (+/- 2 days) after the start of Cycle 1. Other cycles should be started within +/- 4 days of the 3 weekly treatment cycle intervals.
- Cycle 2 and Cycle 4 visits are mandatory.** Cycle 3, 5, 6, 7 and 8 visits are not mandatory; visits every 3 weeks would be preferred, but may be adapted to match local practice.

	Screen ¹	Lapatinib and Capecitabine Cycle ^{9,10}		Withdrawal from Study Treatment or End of Study Visit ¹¹
		1	2 to 8	

11. After 24 weeks treatment with lapatinib and capecitabine. Investigators should continue to treat subjects with lapatinib and capecitabine beyond 24 weeks in accordance with local clinical practice.
12. Serious adverse events and other safety data as described in Section [7.4] of the Study Protocol should be reported for all subjects who continue treatment with lapatinib and capecitabine beyond the 24 week end of study assessment.
13. If more than 12 weeks since the screening cardiac function assessment.
14. If clinically indicated.

One interim analysis was planned when at least 60 subjects have been randomised to treatment and completed their 9 week assessment or discontinued from study. The interim analysis allowed stopping the study early for lack of efficacy (futility) or safety. [Table 1-3](#) described the objectives and endpoints for final analysis. Since study was futile based on the interim analysis results, team decided to create abbreviated CSR for final analysis and hence removed some of the endpoints from final analysis.

The objectives and endpoints of the study are summarized in [Table 1-3](#).

Table 1-3 Objectives and endpoints

Objectives	Endpoints
Primary: Investigator reported	
To determine the efficacy of prophylactic octreotide in reducing the proportion of subjects experiencing diarrhoea with a severity of National Cancer Institute Common Terminology Criteria for Adverse Events (NCI-CTCAE) Grade 2 and above.	Proportion of subjects experiencing diarrhoea with a severity of Grade 2 and above, as defined by the NCI-CTCAE, version 4.03.

Secondary: Investigator reported	
To determine the efficacy of prophylactic octreotide in reducing the proportion of subjects experiencing diarrhoea with a severity of NCI-CTCAE Grade 3 and above.	Proportion of subjects experiencing diarrhoea with a severity of Grade 3 and above, as defined by the NCI-CTCAE, version 4.03, recorded as adverse events (AEs) in the electronic Case Report Form (eCRF).

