3.3 Sample Size Re-estimation

Sample size re-estimation is not planned for this study.

4 Change to protocol specified analyses

Since final CSR will be an abbreviated CSR, not all endpoints will be analysed. [Table 1-3](#) contains reduced list of endpoints as compared to protocol.

Secondary endpoint Patient reported Diarrhoea Management Diary (DMD) is reported using a listing of patients reporting changes in bowel movements from baseline (frequency and/or consistency), recorded in the DMD.

5 Appendix

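### After the futility result the SAP drops five of the eight investigator-reported diarrhoea secondary endpoints without a stated selection rule, so no consequence of diarrhoea is analysed as a diarrhoea-related proportion by randomised arm

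*Protocol*

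**What the plan says.** Protocol Table 7 sets out eight investigator-reported secondary endpoints on diarrhoea. Four describe the diarrhoea itself: Grade 3 and above, any grade, duration, and time to first onset. Four describe its consequences or management: anti-diarrhoeal medication, unscheduled visits, "Proportion of subjects requiring diarrhoea-related lapatinib and capecitabine dose reduction, dose delay and treatment withdrawal, recorded in the eCRF", and "Proportion of subjects requiring use of diarrhoea-related intravenous fluids for rehydration, recorded in the eCRF". Compliance, tumour response and AEs/SAEs are further investigator-reported secondaries outside this group.

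Protocol Section 9.3.3.2 warns that the sample may be too small to show significance on the primary objective, and adds: "The diarrhoea-related secondary objectives of the study will provide additional perspective to support the primary objective". Section 9.3.5.1.2 plans a by-arm analysis of all eight in the ITT and m-ITT populations.

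The SAP was written after the DMC had recommended stopping for futility (SAP Sections 1 and 2.9). Section 1.1 says that the "team decided to create abbreviated CSR for final analysis and hence removed some of the endpoints from final analysis". Section 4 repeats that "not all endpoints will be analysed" and points to the shorter Table 1-3. Section 1 states that decisions on the final analysis preceded database lock.

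**The concern.** The endpoint list was shortened once the primary result was known, and the SAP does not say why some diarrhoea endpoints stayed and others went. All four consequence endpoints went. The protocol's case for prophylaxis (Sections 1.1 and 1.3.2) is that it could spare dose reductions and interruptions, and Section 3.2 allows that octreotide might reduce severity without reducing incidence. A trial stopped at 62 subjects depends more, not less, on supporting endpoints to interpret its primary result. Without them the final report cannot say, by randomised arm, how many subjects had treatment changed, needed IV fluids, made unscheduled visits or took medication because of diarrhoea.

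**Working it through.** **Count.** Protocol Table 7 set against SAP Table 1-3, with what else the SAP offers by arm:

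| Protocol Table 7 endpoint | SAP Table 1-3 | Other SAP output |
|---|---|---|
| Grade 3 and above | kept | not needed |
| Any grade | kept | not needed |
| Time to first onset | kept | not needed |
| Duration | dropped | by-subject listing only (2.6.1.2) |
| Anti-diarrhoeal medication | dropped | concomitant medication by ingredient, no indication (2.4.2) |
| Unscheduled visits | dropped | none |
| Changes to lapatinib/capecitabine | dropped | partial (below) |
| IV fluids | dropped | no diarrhoea-related summary |

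8 − 3 = 5 dropped. Four of the five are consequence measures, which is all four that Table 7 contains.

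**What remains for dose changes.** SAP 2.7.5 tabulates AEs leading to discontinuation of lapatinib and of capecitabine by preferred term, and Section 2.7 makes safety summaries by treatment group. Withdrawal due to diarrhoea is therefore still visible by arm. SAP 2.7.1.2 summarises reductions and interruptions with reasons, but only if there are enough data. The documents do not show whether the reason field names diarrhoea or only an adverse event. SAP 2.7.2 adds an AE overview of dose reductions/interruptions and additional therapy, which is not specific to diarrhoea.

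**Why these are not the protocol's endpoints.** The Section 2.7 outputs use the Safety population. SAP 2.2 moves a subject randomised to octreotide who is intolerant of the s.c. dose, and who then takes lapatinib or capecitabine, into the no-octreotide group. They are not strictly comparisons by randomised arm. Protocol 9.3.5.2.2 would have summarised action taken for diarrhoea AEs. SAP 2.7.3 limits this to counts by preferred term, with worst outcome and maximum grade. The patient diary does not fill the gap, since SAP 2.6.2.1 only lists it.

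**Are the data collected?** Yes. Protocol Section 6.1 requires anti-diarrhoeal medication to be recorded. Sections 7.1.5, 7.1.6 and 7.1.8 require diarrhoea-associated visits or contacts and IV rehydration. Sections 7.1.6 and 7.1.8 require diarrhoea-associated delays and reductions. Section 7.1.7 requires unscheduled visits and their reasons.

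**Precision.** 62 were enrolled; assume 62 / 2 = 31 per arm.

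- Illustrative 20% v 10%: Wald half-width = 1.96 × √(0.2 × 0.8/31 + 0.1 × 0.9/31) = 0.176, about ±18 points. The smallest expected cell is 31 × 0.15 = 4.65, so SAP 5.3.1, which wants expected values above 5, calls for exact limits. The Wald figure is only a rough guide.
- Rates from the protocol's own background: in EGF111438 the text gives 16 subjects with interruption due to diarrhoea, and Table 4 sums to 16 + 1 + 2 = 19, out of 269. At 31 per arm that is 31 × 16/269 = 1.8 to 31 × 19/269 = 2.2 subjects. Withdrawal due to diarrhoea was 1 of 269 there and 5% in EGF100151, giving 31 × 1/269 = 0.1 to 31 × 0.05 = 1.6 subjects.

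**The case against.** The strongest reply is that the cut is open, reasoned and proportionate. It is declared in SAP Sections 1, 1.1 and 4, and tied to a trial stopped for futility and an abbreviated report. SAP 5.1 provides for a team review of which analyses remain appropriate if the study is terminated. Three diarrhoea endpoints stay, and counts for the others would be small. Much of this stands, and it limits the point in three ways.

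- A reader might infer that nothing by arm survives on dose changes or medication. The documents do not support that: discontinuations stay by preferred term, reductions and interruptions are conditionally summarised with reasons, and loperamide users would appear in the ingredient table.
- A reader might infer selective reporting. Nothing shows that by-arm results on the dropped endpoints were seen or guided the choice. Protocol 9.3.4 describes interim review of the primary endpoint, a Grade 3 interval and safety data.
- A reader might take Section 9.3.3.2 to make these endpoints indispensable. It promises additional perspective, and the three retained endpoints still supply some of it.

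What does not stand as an answer: the lock mentioned in Section 1 is the final one, after the interim result was known. SAP 5.1 also says that all available data will be listed on termination, yet the SAP names no listing of diarrhoea-related visits or IV fluids. Declaring a reduction does not explain which endpoints were chosen.

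**Conclusion.** The point holds as a cheap improvement. Five of the eight investigator-reported diarrhoea secondaries were removed after the futility result, with no stated rule for selection, and all four consequence endpoints are among them. For visits and IV fluids, no diarrhoea-related by-arm summary remains. For dose changes and medication only indirect summaries remain, and duration is only listed. This is a gap in reporting and in the stated rationale; it does not show that the result was steered.

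The count rests on the two tables alone. The judgement on dose changes depends on an eCRF reason field that the documents do not show. The precision figures assume 31 per arm and illustrative or background rates. They show that the restored estimates would be imprecise and, for interruptions and withdrawals, possibly based on one or two subjects per arm. That argues for descriptive reporting without tests.

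**What to change.** Add to SAP 2.6.1 descriptive by-arm summaries of the five endpoints in the ITT population over the entire treatment period, the window already used for the retained Grade 3-and-above and any-grade endpoints.

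- **Four proportions** (medication, visits/contacts, changes to lapatinib or capecitabine, IV fluids): n/N (%) per arm and the difference with 95% CI by the SAP 5.3.1 method, using exact limits where an expected count is 5 or less.
- **Duration:** median and quartiles per arm.
- **No hypothesis tests.**

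Keep the definition in protocol 9.3.5.1.2, "requiring an unscheduled visit to or contact with a healthcare professional at least once as a result of diarrhoea", and show visits and contacts separately if the eCRF allows. Appendix 1 wants subjects told to "first notify their physician/healthcare provider at onset of diarrhoea of any severity", so contacts may track any-grade diarrhoea; a split would let the reader see this without changing the definition. If any endpoint still stays out, Section 4 should name it and give the reason.

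The cost is up to five extra tables in the abbreviated report, from data the protocol already requires in the eCRF, with imprecise estimates.

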**Table 8 National Cancer Institute common terminology criteria for grading diarrhoea adverse events**

Adverse Event Grade	Diarrhoea
1	Increase of <4 stools/day over baseline; mild increase in ostomy output compared to baseline
2	Increase of 4-6 stools/day over baseline; moderate increase in ostomy output compared to baseline;
3	Increase of $\geq 7$ stools/day over baseline; incontinence; hospitalisation indicated; severe increase in ostomy output compared to baseline; limiting self care activities of daily living
4	Life-threatening consequences; urgent intervention indicated
5	Death

Data will be recorded by the investigators in the eCRF at each study visit and by subjects in the DMD every week and in the FACIT-D every 3 weeks. These are considered to be independent sources of study data, and investigators must not use information collected in the DMD and FACIT-D to supplement data entry into the eCRF. Where comparable data are collected in the eCRF and in the DMD, secondary endpoints will be evaluated to contrast and compare these data within each treatment group, although differences between the eCRF data and the PRO data will preclude formal comparisons.

All subjects will complete the baseline DMD and the FACIT-D during the 3 days prior to randomisation, before any study-related treatment is administered. Subjects randomised to receive octreotide will complete a second baseline DMD and the FACIT-D before starting the first cycle of treatment with lapatinib and capecitabine. Hence, subjects randomised to receive octreotide will complete the baseline DMD and the FACIT-D (Week -1) prior to receiving the first dose of octreotide (0.1mg subcutaneous tolerability test dose), and all subjects will complete the baseline DMD and the FACIT-D prior to receiving the first dose of lapatinib and capecitabine (Week 0).

The DMD will be completed every week after the first dose of lapatinib and capecitabine is administered (Week 1, Week 2, Week 3, etc), until the end of study visit (Week 24, disease progression, unacceptable toxicity or subject withdrawal if this is sooner). The FACIT-D will be completed every 3 weeks during treatment with lapatinib and capecitabine (Week 3, Week 6, Week 9, etc), until the end of study visit (Week 24, disease progression, unacceptable toxicity or subject withdrawal if this is sooner). The DMD and FACIT-D will not be completed beyond 24 weeks of treatment.

The baseline DMD comprises 3 questions to record stool form and consistency. The DMD to be completed throughout the rest of the study comprises the 3 questions in the baseline DMD and a further 5 questions and 6 sub-questions to evaluate the consequences and management of diarrhoea. A copy of the baseline DMD and the DMD is included in the Study Procedures Manual (SPM).

The FACIT-D ([Appendix 2](#)) comprises the 27 item Functional Assessment of Cancer Therapy-General (FACT-G) questionnaire which has physical (PWB), social (SWB), emotional (EWB) and functional wellbeing (FWB) subscales and an 11 item diarrhoea symptom subscale (DSS) which measures quality of life specific to diarrhoea. The primary endpoint derived from the FACIT-D will be the Trial Outcome Index, which is a summation of the PWB, FWB and diarrhoea symptom subscales. Secondary endpoints will be overall quality of life (total FACT-G), total FACIT-D and scores from each of the individual subscales.

Disease progression in accordance with RECIST version 1.1 is required only at the end of study visit. Disease assessments during the course of treatment with lapatinib and capecitabine may be conducted in accordance with local practice. The assessment of disease progression in LAP117314 is less rigorous than that employed in EGF100151 and EGF111438. LAP117314 is an exploratory study, and disease efficacy data may not be comparable with that reported in other studies.

### **3. INVESTIGATIONAL PLAN**

#### **3.1. Study Design**

This is a randomised, parallel group, multi-centre, open-label Phase II study in subjects with HER2-positive metastatic breast cancer which has progressed following prior therapy, which must have included anthracyclines and taxanes and therapy with trastuzumab in the metastatic setting. This study is not placebo controlled, and there is no active comparator.

Protocol waivers or exemptions are not allowed with the exception of immediate safety concerns. Therefore, adherence to the study design requirements, including those specified in the Time and Events Schedule ([Table 16](#), and [Table 17](#)), is essential and required for study conduct.

Supplementary study conduct information not mandated to be present in this protocol is provided in the accompanying SPM. The SPM will provide the site personnel with administrative and detailed technical information that does not impact subject safety.

Subjects must be screened for eligibility and informed consent must be given before any study-related procedures are conducted.

All subjects will receive treatment with lapatinib 1250mg once daily and capecitabine 1000mg/m^2 twice daily until disease progression. Lapatinib will be given every day; capecitabine will be given in 3 week cycles of two weeks treatment followed by one week off treatment.

Subjects will be randomised in a 1:1 ratio to receive either:

- Octreotide (Sandostatin LAR) 40mg 7 days before the start of treatment with lapatinib and capecitabine and again 28 days later, or
- No octreotide treatment.

For subjects randomised to receive octreotide, treatment with lapatinib and capecitabine will be initiated 7 days after the first dose of octreotide given as the LAR formulation. For subjects randomised to receive no octreotide, treatment with lapatinib and capecitabine will be initiated immediately following enrolment.

Subjects randomised to receive octreotide LAR must be given one 0.1mg dose of the standard formulation of octreotide s.c. to assess tolerability at least one hour before the first dose of the LAR formulation is administered. Subjects with significant intolerance to octreotide 0.1mg s.c. will not receive treatment with octreotide LAR, but will receive treatment with lapatinib and capecitabine as scheduled.

All subjects with episodes of diarrhoea will be encouraged to follow the GSK diarrhoea management guidelines for subjects receiving lapatinib ([Appendix 1](#)). In subjects randomised to receive octreotide, episodes of mild diarrhoea which occur following the first dose of octreotide LAR should be managed in accordance with the diarrhoea management guidelines. The use of octreotide in the s.c. formulation for the management of diarrhoea refractory to treatment with loperamide is not excluded. Investigators should use their clinical judgement concerning the use of octreotide s.c. in subjects randomised to receive treatment with octreotide LAR, particularly during Week 2 through to Week 12 of treatment with lapatinib and capecitabine, when circulating concentrations of octreotide should already be within the clinically effective range.

Subjects who report constipation with a severity of NCI CTCAE Grade 2 and above ([Table 9](#)) following the first dose of octreotide LAR must not receive the second dose of octreotide LAR, but will continue to receive treatment with lapatinib and capecitabine as scheduled.

